### B1. PURPOSE OF PROTOCOL

The purpose of this study is to determine the effects of a web based intervention called “Inner Engineering Online (IEO)” on the burnout states, stress and overall well-being of employees in a company.

The specific aims include:

1. To test feasibility and acceptance of IEO through assessment of participation, compliance, protocol adherence & study satisfaction.
2. To quantitatively assess the effects of IEO on measures of Burnout, Stress & well-being among the participating employees.
3. To determine the effect of IEO on measures of well-being among control employees after they cross over to the intervention group at the end of first phase.

### B2. SIGNIFICANCE AND BACKGROUND FOR THE STUDY

Burnout is described as a syndrome resulting from chronic workplace stress that has not been successfully managed. It is characterized by exhaustion, depersonalization, and reduced professional efficacy. Several studies have evaluated interventions that are aimed at identifying and ameliorating burnout, or components of burnout such as high stress and sleep disturbances. Meditation, specifically, has shown to be an accessible and efficient method for combating stress, burnout, and promoting a sense of well-being.

Inner Engineering Online (IEO) is a web based intervention administered by the Isha Foundation, a not-for-profit, global, volunteer-based organization. IEO is widely practiced around the globe, but lacks a systematic evidence base. The Inner Engineering Online program is a holistic tool for promoting well-being that teaches individuals how to mindfully and effectively respond to daily stressors using yogic sciences. The program offers guided meditation and yoga practices to promote harmonizing mind-body-emotion and energy of the individual while simultaneously promoting mindfulness, joy, and vitality.

Studies reveal that Inner Engineering meditation and yoga practices improve mental clarity, emotional well-being, productivity, and inner peace while reducing perceived stress and compulsive behaviors. These studies suggest that practice of Inner Engineering meditation may be a pragmatic treatment for stress reduction.

S2Tech is a reputed company providing Information Technology (IT) support to businesses in 35 states of United States of America for over 22 years. The company is looking to promote mindfulness and combat burn out and stress in its employees while voluntarily supporting research studies assessing these markers. The Company is offering the standalone Inner Engineering Online (IEO) course from Isha foundation for all its interested employees primarily to combat stress. While the participants are encouraged to participate in this study, research participation is entirely optional for the participants and will not impact their relationship with their employees in any form. The primary purpose is for the company to offer programs to combat stress and research is optional.

In this randomized controlled trial, differences in overall stress, burnout and wellbeing will be assessed for employees participating in IEO, an online mind-body course that incorporates both meditation and yoga.

The following specific aims are to be accomplished via this study:

- **Specific Aim 1:** To test the feasibility and acceptance of Inner Engineering Online through assessment of participation, compliance, protocol adherence and study satisfaction.
- **Specific Aim 2:** To quantitatively assess the effect of IEO on measures of burnout, stress, and well-being among study participants.
- **Specific Aim 3:** To determine the effect of IEO on measures of well-being among the control-group after they cross-over to the intervention group at the end of first phase.

The study will be conducted in 2 phases. The first phase will accomplish specific aims 1 and 2, while specific aim 3 will be accomplished in the second phase.

References:

1. WHO. Burn-out an “occupational phenomenon”: International Classification of Diseases [Internet]. 2019 May 28. Available from: [https://www.who.int/mental\\_health/evidence/burn-out/en/](https://www.who.int/mental_health/evidence/burn-out/en/)

### B3. DESCRIPTION OF RESEARCH PROTOCOL

#### A. Study Design – Overview, Methods, Procedures

##### Study Overview:

This study involves evaluation of the effects of Inner Engineering Online (IEO) intervention by employing validated questionnaires aiming to measure stress and well-being in the form of a survey to company employees participating in the study.

In order to evaluate this, we randomize the participants into either of the two groups: one who participate in the IEO activities daily for the first 30 days and the other who do not participate in the IEO activities during the first 30 days. We then evaluate stress and burnout along with measures of well-being in these participants using validated electronic instruments at baseline and at the end of the 30 days. This is phase 1 of the study.

For the phase 2, we cross-over the group 2 participants and provide them with the IEO intervention. We follow them through another 30 days and then evaluate measures of stress, burnout and well-being using validated instruments at the end of these 30 days.

### **Enrollment:**

The recruitment is done by the S2Tech company using flyers for advertisements at the company. The recruitment process also involves awareness campaigns, word of mouth announcements as well as advertising flyers on the social media and official websites of the company.

The research team sends a public survey link, where participants can confirm their interest in the study and get detailed information of the study procedures after the company recruits potential participants during awareness campaigns organized by the company.

If they are interested in participating after receiving the email, they will be directed to REDCap where they will be asked a few screening questions to ensure study eligibility. Participants who are eligible will then be directed to an electronic consent form.

### **Randomization:**

Participants will be randomized into one of the two groups using [Simple Randomization Technique] by REDCap. Participants will be randomized into:

1. Intervention Group: Participants will receive the Inner Engineering Online Intervention for a total of 30 days (4 weeks)
2. Control Group: Participants will read a book/journal of their choice for 25 minutes each day for a total of 30 days (4 weeks)

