### **Study Procedure:**

We will be administering a brief survey to willing participants after they provide electronic consent. If a participant decides to participate, they will receive a paper survey to complete, or they can complete the survey online via an anonymous REDCap survey link.

The Isha Foundation (which is responsible for the Inner Engineering Online Course) has agreed to send participants an email which contains detailed instructions on how to perform the IEO intervention after the electronic consent has been signed. The Isha Foundation receives the participating employee emails from the company, as they are the primary instructors for the intervention.

Subjects will be randomized following the consent into two groups.

**Group 1** will be asked to complete the Inner Engineering Online course which includes completing 7 meditation and yoga course modules in a duration of 30 days. They will be given an IEO activity diary and will be asked to keep a track of their progress. The activity diary will be collected from them on a

weekly basis for 30 days.

After 4 weeks (i.e., 30 days) they will be administered the same set of survey questionnaires which was asked before the intervention was administered. All communications will be conducted electronically or via phone.

**Group 2** will be asked to read a book or journal of their choice for 30 minutes at a time for 30 days. They will also be asked to complete a reading log every day to keep a track of their progress every day for 30 days.

Once 30 days is over they will be asked to complete the IEO intervention, which includes practice of meditation and yoga daily for another 30 days while maintaining an IEO activity diary. Group 2 will be asked to complete set of questionnaire at baseline, 30 days and after 60 days.

Surveys will be administered at two time points for group 1 at baseline and at 30 days, whereas three time points for group 2 that is baseline, 30 days and 60 days.

Apart from the surveys, the participants are advised to maintain a reading log or an activity diary for each week. These documents will be collected electronically, either via direct online submission or a scanned copy to be uploaded and sent to a redcap survey link at the end of each week. In order to account for national holidays and personal circumstances, participants may submit their activity diaries and/or reading logs within 2 weeks of the 30 day and 60 day time point.

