## B. Statistical Considerations

### a. *Sample Size Justification:*

In this survey based, randomized cross-over study, we are looking at the feasibility of implementing an Inner Engineering Online Intervention on a group of willing company employees. Since it is a feasibility study, we plan to enroll a minimum of 60 participants. Data from these participants will be used to power a larger trial based on the outcomes such as stress, burnout & overall well-being measured during the course of the study.

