#### **Analysis of Aim 1:**

Trial feasibility and adherence will be assessed using data from how often participants in the intervention group complete their IEO activities. This would be reported as the proportion of completed activities out of the total required per protocol. Similar analysis would be done for the control group and adherence to protocol too would be ascertained as a proportion of instance of protocol deviation out of total required activity per protocol. Participant satisfaction will be measured using an internally developed survey. Continuous and dichotomous data will be reported and assessed in a similar fashion as above.

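### Nothing in the protocol makes a submitted baseline survey a condition of allocation; separately, simple randomisation at the minimum of 60 leaves arm sizes to chance, at a modest cost.

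*Combined protocol and SAP*

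**What the plan says.** **Allocation.** B3.A, Randomization: "Participants will be randomized into one of the two groups" "using [Simple Randomization Technique] by REDCap". No blocks, strata or allocation ratio are given. B3.B, Sample Size Justification: "Since it is a feasibility study, we plan to enroll a minimum of 60 participants". There is no minimum per arm.

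**Order of baseline and allocation.** Three places in B3.A bear on this:

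- Study Overview describes randomising into two groups first, then evaluating stress, burnout and well-being at baseline and at 30 days.
- Study Procedure opens with the survey: "We will be administering a brief survey to willing participants after they provide electronic consent". Further down it says: "Subjects will be randomized following the consent into two groups".
- For Group 1, Study Procedure describes the 30-day survey as "the same set of survey questionnaires which was asked before the intervention was administered".

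**Survey route.** Study Procedure lets a participant complete the survey through an online link described as anonymous, or on paper ("they will receive a paper survey to complete").

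**Use of the data.** Aim 1 reports adherence from "data from how often participants in the intervention group complete their IEO activities", with a similar analysis in controls. Aim 2 compares the groups by t-test, with optional adjusted regression, and uses paired tests against baseline. Aim 3 concerns the control group after cross-over, with the same set of methods.

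**The concern.** A baseline value can serve as a covariate or as the start of a change score because allocation cannot have affected it. That holds only if it is recorded before the participant knows the arm. Here the two arms are IEO and reading, which participants cannot fail to tell apart. Interest in IEO is an inclusion criterion, so assignment to reading means a 30-day wait for something the person wanted. Every outcome scale is self-reported. Someone who rates stress or burnout just after learning the arm may rate it differently because of that news. The difference would then enter the paired tests and any baseline-adjusted regression. The data are also meant to inform the power of a larger trial, so a distorted change score could be carried forward.

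The second issue is smaller. Simple randomisation of about 60 people can leave one arm noticeably short. The Aim 2 comparison tolerates this well. The cross-over analysis (Aim 3, control arm) and IEO adherence in the first phase (Aim 1, intervention arm) each depend on the size of one arm.

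**Working it through.** **1. Is baseline before allocation secured?** Setting the statements side by side:

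| Place (B3.A) | What it fixes | What it leaves open |
|---|---|---|
| Study Overview | Mentions randomisation, then baseline evaluation | Whether this is strict order or loose narrative |
| Study Procedure, survey sentence | Survey comes after consent | Order relative to randomisation |
| Study Procedure, randomisation sentence | Randomisation comes after consent | Order relative to the survey |
| Study Procedure, Group 1 | Baseline comes before the intervention | Whether it comes before the arm is known |

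Consent precedes both steps, and baseline precedes the intervention. No statement places a submitted baseline before allocation. An anonymous response, read literally, also could not confirm that a given person had finished.

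**2. What would a post-allocation baseline do?** The documents give no figure, so the following are assumptions. Let a fraction f of controls answer after learning their arm and report baseline stress d SD higher as a result. The control baseline mean rises by f × d.

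- Difference in change scores: shifts by f × d. With d = 0.2: f = 1 gives 0.20 SD, f = 0.5 gives 0.10 SD, f = 0.25 gives 0.05 SD.
- Baseline-adjusted difference: shifts by b × f × d, where b is the slope of follow-up on baseline. With f = 1, d = 0.2 and b = 0.5, this is 0.5 × 0.2 = 0.10 SD. It is below 0.20 SD whenever b lies between 0 and 1.
- Group 1 paired change: no shift under this assumption.
- Comparison of 30-day scores alone: no shift.
- Control comparison of day 30 with day 60: no shift.

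Inflated control baselines would make controls appear to improve more, and so understate an IEO benefit. Other reactions could act the other way, so the direction is not established.

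**3. Arm sizes.** Inputs: N = 60 (Sample Size Justification, a minimum) and simple randomisation (Randomization section). A 1:1 ratio is assumed because none is stated. The figure of 60 has no power or precision calculation behind it to reproduce. One arm's size X is then Binomial(60, 0.5).

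- P(X ≤ 24) = 7.8% for a named arm; for either arm, 2 × 0.0775 = 15.5%.
- P(X ≤ 22) = 2.6% for a named arm; 5.2% for either.
- P(exactly 30/30) = 10.3%.

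Variance relative to 30/30 is 30/a for a single arm of size a, and 15 × (1/a + 1/(60 − a)) for the between-arm difference.

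| Split | Smaller arm | Larger arm | Between arms |
|---|---|---|---|
| 24/36 | 30/24 = 1.25 | 30/36 = 0.83 | 1.042 |
| 22/38 | 30/22 = 1.36 | 30/38 = 0.79 | 1.077 |

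Averaged over all splits, the between-arm ratio is 1.018. By symmetry the single-arm average is the same, because E[15(1/X + 1/(60 − X))] = 30 E[1/X]. The average loss is therefore about 1.8% in variance on either measure, and the 25% and 36% are tail cases.

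Practical effect of an arm of 24 instead of 30:

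- 95% half-width for an adherence proportion, 1.96 × √(p(1 − p)/n): 14.3 to 16.0 points at an assumed p = 0.8, and 17.9 to 20.0 points at p = 0.5.
- Paired effect detectable with 80% power (assumed) at two-sided 0.05: 0.53 to 0.60 SD.

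The chance that the smaller arm holds 40% or less of the total falls from 15.5% at N = 60 to 9.3% at N = 80 and 5.7% at N = 100.

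**4. Under permuted blocks.** With randomly varying blocks of 4 and 6, the 60th participant falls at the end of a block, or after 2 or 4 places in an unfinished one. The largest difference between arms is then 2, so the worst split is 29/31. At 29 the half-width is 14.6 points (p = 0.8) and the detectable paired effect about 0.54 SD.

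**The case against.** On timing, the other side says this is a gap and not an error. Study Procedure describes the survey before it mentions randomisation and places the questionnaires before the intervention, so the team may well intend baseline first. That is fair. A reader might infer from the Study Overview that baseline is planned after allocation, but a loose narrative order does not establish that. What stands is that the order is unclear and nothing enforces it.

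A reader might also infer that every paired or baseline-adjusted result would be biased. Under the control-arm shift assumed above, Group 1's paired change is untouched, and so are a comparison of 30-day scores and a day-30 to day-60 comparison in controls. Nor do the documents say that paper baselines will come back late. They allow paper, give no return window, and elsewhere describe electronic instruments and direct entry into REDCap.

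On arm sizes, the objection largely succeeds. Pairing the 15.5% either-arm probability with a single-arm penalty overstates the risk to Aim 3, for which 7.8% is the relevant figure. When one arm is short the other gains. Aim 1 also reports adherence in controls, so it does not rest wholly on one arm. Sixty is a minimum, and no precision target exists to be missed. A reader might add that stress varies over the calendar and simple randomisation fails to balance it. The documents give no accrual period and no such pattern, and any imbalance would be chance, not bias. Simple randomisation is also the least predictable scheme in an open trial. What remains is a small, cheap gain in guaranteed arm size.

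**Conclusion.** The concern holds in a limited form, as an inexpensive improvement and not a fatal flaw. The timing gap is the stronger part: the protocol does not make a submitted baseline a condition of allocation, in an open trial with self-reported outcomes and participants who all want IEO. Its effect is possible but unquantified. The 0.2 SD figure is an assumption, reached only if all controls shift by that amount, and it applies to change scores, with a smaller effect on adjusted contrasts.

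The arm-size part is minor. At N = 60 with an assumed 1:1 ratio, one or other arm has 24 or fewer with probability 15.5%, and a named arm with probability 7.8%. The average variance loss is about 1.8%, and the risk falls as enrolment rises above 60.

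**What to change.** **B3.A, Study Overview and Study Procedure.** State that randomisation takes place only after the participant's baseline survey has been submitted, and set REDCap to enforce this. Replace the anonymous survey link with one tied to the study ID that Data Security (B8) already provides for; otherwise REDCap cannot tell whether a given person has completed baseline. State that any paper baseline is entered before allocation is released.

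**B3.A, Randomization.** Replace simple randomisation with concealed permuted blocks of randomly varying size, for example 4 and 6, and state the allocation ratio.

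**Cost.** REDCap setup work, a few sentences of text and no extra participants. Blocking gives up a little unpredictability compared with simple randomisation; keeping the block sizes varying and undisclosed limits this. The timing change is worth making even if blocking is declined.

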**Reading Log:**

The reading log is a tool which helps the participants to keep a track of their reading each week. This enables the study team to measure compliance and protocol adherence by the participants.

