### b. *Data Analysis:*

Baseline characteristics of participants will be recorded. Continuous data will be presented as means  $\pm$  standard deviation or median (interquartile range) depending on the distribution of the data and assessed with a parametric or non-parametric t-test, as appropriate. Normality will be assessed with the Shapiro-Wilk test. Categorical data will be presented as frequencies and proportions and assessed with a chi-square or Fisher's exact test. SAS 9.4 (SAS Institute Inc., Cary, NC) will be used for all analyses with two-sided p-values  $< 0.05$  considered statistically significant.

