#### **Analysis of Aim 2:**

Given the continuous nature of the scales used to assess stress, burnout and measures of well-being, differences between groups will be assessed with a parametric or non-parametric t-test. Although we expect that randomization should account for any differences between baseline characteristics, unadjusted and adjusted linear regression may be utilized in order to account for differences that persist. Our primary analyses will be assessed using intention-to-treat principles. In order to assess whether there are differences between baseline and at six weeks, we will employ the use of paired t-tests as appropriate.

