### C. Subject Selection

#### Inclusion Criteria:

- Age  $\geq$ 18 years
- Interest in Inner Engineering Online (IEO) Program

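### Control reading has no topic limit, so controls enrolled for their interest in IEO could read meditation or stress-management material and count as fully adherent, which could bias the Aim 2 difference toward no effect

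*Combined protocol and SAP*

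**What the plan says.** The control task is described twice in section B3.A, each time without a limit on content. Randomization says "Participants will read a book/journal of their choice for 25 minutes each day". Study Procedure says Group 2 "will be asked to read a book or journal of their choice for 30 minutes at a time for 30 days". The durations differ (25 and 30 minutes). That is a separate inconsistency, which the sponsor should reconcile.

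The only restriction on controls in phase 1 is in Study Overview, which describes them as "the other who do not participate in the IEO activities during the first 30 days". Related reading does not breach it.

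One of the two inclusion criteria is "Interest in Inner Engineering Online (IEO) Program", and it applies to both arms.

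Monitoring is by log: "The reading log is a tool which helps the participants to keep a track of their reading each week". The stated purpose is to measure compliance and adherence. No section says that topic is recorded or reviewed, and the log template is not in the documents. Analysis of Aim 1 reports control adherence as a proportion of the required activity.

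For Aim 2, "differences between groups will be assessed with a parametric or non-parametric t-test", and "Our primary analyses will be assessed using intention-to-treat principles". No sensitivity analysis for what controls read is planned. Under Sample Size Justification, the data are to be used to power a larger trial.

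**The concern.** These rules combine awkwardly. People who volunteered because a stress-reduction course interested them are told to read something every day while they wait for it. A book on mindfulness or stress management is a natural choice for some of them, and nothing in the plan discourages it or would flag it.

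The content could overlap with the intervention. Section B2 describes IEO as partly instructional: it teaches people how to respond to daily stressors, alongside guided practice. The outcomes include a mindfulness scale (MAAS), perceived stress (PSS) and burnout (MBI), which are what such books address.

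If related reading has any benefit, the control mean moves in the same direction as the intervention mean and the difference narrows. Under intention-to-treat these controls rightly stay in their arm. A small or null Aim 2 result would then be harder to interpret, because the content of the comparator might not be known.

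**Working it through.** **The plan's own figure.** The minimum enrolment of 60 is justified by feasibility alone. The plan gives no effect size, SD, power or dropout, so there is no power calculation to reproduce.

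**The text, step by step.**
1. Are controls selected for interest in IEO? Yes (Inclusion Criteria).
2. Is their reading limited by topic? No (Randomization, Study Procedure).
3. Does the ban on IEO activities cover related reading? No (Study Overview).
4. Would such reading lower measured adherence? Not as written: the log tracks reading, and Analysis of Aim 1 counts completed activity.
5. Does the Aim 2 analysis address it? No.

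**Illustration of size.** Let f be the share of controls who read related material and s the share of the IEO effect they gain from it. The control mean then moves by f × s × d, so

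observed d = d × (1 − f × s).

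The documents give neither f nor s. Assumed ranges are f = 0 to 0.30 and s = 0 to 0.50. Other assumptions are 1:1 allocation (the ratio is not stated), hence 30 per arm; a true d of 0.5; two-sided alpha of 0.05 as in Data Analysis; and the normal approximation.

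- Standard error of the difference, in SD units: √(2/30) = 0.258.
- Power: Φ(observed d / 0.258 − 1.960).
- n per arm for 80% power: 2 × (1.960 + 0.842)² / d² = 15.70 / d².

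| f | s | Shrinkage | Observed d | Shift / SE | Power, 30 per arm | n per arm, 80% power |
|---|---|---|---|---|---|---|
| 0, or s = 0 | – | 0% | 0.500 | 0 | 49% | 63 |
| 0.10 | 0.25 | 2.5% | 0.4875 | 0.0125/0.258 = 0.05 | 47% | 15.70/0.2377 → 67 |
| 0.30 | 0.50 | 15% | 0.425 | 0.075/0.258 = 0.29 | Φ(−0.314) = 38% | 15.70/0.1806 → 87 |

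The required sample size scales as 1/(1 − f × s)². That is 1/0.975² = 1.05 in the middle row and 1/0.85² = 1.38 in the last.

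Total control reading time is 30 × 25 = 750 minutes, or 30 × 30 = 900 on the other stated duration. That is reading of any kind. It does not measure exposure to related material and does not enter the calculation.

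**The case against.** The strongest reply is that the mechanism is conjecture. Nothing in the documents says controls will choose such books, and they are promised IEO itself after 30 days. The intervention is largely practice, and reading about meditation is not practising it. No source in the plan shows that such reading moves MAAS, PSS or burnout scores. This stands, and it is why zero belongs in the range. It does not remove the gap: the choice is open, the population is selected for interest, and the plan does not say that topic will be known.

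Second, even the largest illustrated shift is under 0.3 of a standard error in a feasibility study with no powered Aim 2 hypothesis. That also stands and limits the weight of the point.

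Third, a topic ban has vague edges, someone must classify titles, and naming the topics may draw controls' attention to them. These costs are real but small.

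Two stronger readings are tempting, and the documents support neither:
- A reader might infer that the effect sizes carried to the larger trial will be too small. That requires controls to choose such reading, the reading to work, and the larger trial to use a different control. If it kept free-choice reading, an estimate against that control would be the right planning input. The documents do not describe that trial's control.
- A reader might infer that Aim 3 is distorted because controls start IEO from an altered day-30 value. Analysis of Aim 3 does not name day 30 as its starting value; it refers to baseline and six weeks. Nor would improvement move every scale the same way: a benefit would lower PSS.

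Study Procedure also has IEO instructions emailed to participants after consent without expressly limiting this to Group 1. That may be a more direct route to contamination, but it is a separate point.

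**Conclusion.** The point holds in conditional form. As written, controls selected for interest in IEO may read meditation, yoga, mindfulness or stress-management material and be fully adherent. If some do, and it affects the scales, the Aim 2 difference could be biased toward no effect.

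The size cannot be derived from the documents. The illustrative 0-15% shrinkage rests on two assumptions with no anchor in the plan, and the true figure may be zero. The power and sample-size figures further assume d = 0.5 and equal arms of 30. This is a worthwhile low-cost improvement that makes the comparator interpretable. It is not a defect that invalidates the Aim 2 analysis.

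**What to change.** 1. In Randomization and in Study Procedure, add to the description of the control reading: *other than material on meditation, yoga, mindfulness, stress management or the IEO programme*.
2. Make sure the reading log captures title or topic. The template is not in the documents and may already do so; if not, add one field.
3. In Analysis of Aim 1, report reading of excluded material as a control-arm deviation, giving the number and proportion of controls. This leaves the Aim 2 estimate unchanged but shows how much exposure there was.
4. Keep the intention-to-treat comparison as the primary Aim 2 analysis.

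The cost is one clause in two places, at most one log field, and a brief check of logged titles by the study team. Controls lose a little free choice. No visits, participants or outcome measures are added. Topic should be recorded prospectively, because it cannot be reliably reconstructed later.
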